5.12 Missing Values – Missing Visits

Missing, unused and spurious data will be considered missing at random and dealt with as such. There is no intention to implement any procedure for replacing missing data.

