5.8.1 Adverse events

The AE reporting period will begin following the first dose of BGB324 (Run-in Cohort) or erlotinib (Arms A, B and C) and will end 28 days after the last dose of BGB324.

The number and percentage of patients reporting TEAEs will be tabulated by Medical Dictionary for Regulatory Activities (MedDRA) preferred term and system organ class, and summarized by CTCAE grade and relationship to study drug. All AEs commencing prior to dosing with study medication will be excluded from the tabulation but will be fully listed.

A subject with more than one occurrence of the same adverse event in a particular system organ class will be counted only once in the total of those experiencing adverse events in that particular system organ class. If a subject experiences the same adverse event at more than one severity, or with more than one relationship to study drug, the most severe rating or the stronger causal relationship to study drug will be given precedence. For example, if the event of multiple occurrences of the same adverse events being reported by the same subject, the maximum intensity (Grade 5 > Grade 4 > Grade 3 > Grade 2 > Grade 1 > missing > not applicable) and the most serious causality (related > not related) will be chosen.

Any missing severity, causality, or outcome will not be imputed and classed as unknown.

An overall summary classifying subjects with events according to seriousness, severity, maximum relationship to BGB324, and maximum CTCAE grade will also be presented.

Related events are defined as events that are ticked as suspected by investigator in eCRF .

Treatment-Emergent AEs are any AEs that start or worsen after first dose of study drug regardless of causality. AEs with partial onset dates will be assumed to have the latest possible onset date (while accounting for stop date) for determining treatment emergence, but no formal imputation will be done. AEs that have missing onset dates will be considered to be treatment-emergent, unless the stop date is known to be prior to the first administration of study drug (BGB324 or Erlotinib whichever comes first).

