6.1.3 Section 14.3: Safety

6.1.3.1 Adverse events

Table 14.3.1.1	Summary of Adverse Events (Safety Population)
Table 14.3.1.2.1	Adverse Events by System Organ Class and Preferred Term (Safety Population)
Table 14.3.1.2.2	Adverse Events by System Organ Class, Preferred Term, and CTCAE Grade (Safety Population)
Table 14.3.1.2.3	Adverse Events Related to BGB324 by System Organ Class and Preferred Term (Safety Population)
Table 14.3.1.2.4	Adverse Events Related to Erlotinib by System Organ Class and Preferred Term (Safety Population)
Table 14.3.1.2.5	Adverse Events by System Organ Class, Preferred Term and Severity of CTCAE Grade (Safety Population)
Table 14.3.1.3.1	Serious Adverse Events by System Organ Class and Preferred Term (Safety Population)
Table 14.3.1.3.2	Serious Adverse Events by System Organ Class, Preferred Term, and Severity of CTCAE Grade (Safety Population)
Table 14.3.1.3.3	Serious Adverse Events Related to BGB324 by System Organ Class and Preferred Term (Safety Population)
Table 14.3.1.3.4	Serious Adverse Events Related to Erlotinib by System Organ Class and Preferred Term (Safety Population)
Table 14.3.1.4.1	Adverse Events Leading to Discontinuation by System Organ Class and Preferred Term (Safety Population)

Table 14.3.1.5.1	Adverse Events with CTCAE Grade ≥ 3 by System Organ Class and Preferred Term (Safety Population)
Table 14.3.1.5.2	Adverse Events \geq Grade 3 Related to BGB324 by System Organ Class and Preferred Term (Safety Population)
Table 14.3.1.5.3	Adverse Events \geq Grade 3 Related to Erlotinib by System Organ Class and Preferred Term (Safety Population)
Table 14.3.1.6.1	Adverse Events Occurring $\geq 10\%$ by System Organ Class and Preferred Term (Safety Population)
Table 14.3.1.7.1	Adverse Events leading to death by System Organ Class and Preferred Term (Safety Population)
Table 14.3.1.8.1.1	Summary of DLTs occurring during the study (Safety Population)

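### Adverse events with missing causality or grade fall outside the related and Grade 3 or higher tables, which may then understate toxicity; SAP 5.8.1 should say how such events are counted

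*SAP*

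**What the plan says.** The operative text is SAP 5.8.1 (Adverse events). On missing attributes it states: "Any missing severity, causality, or outcome will not be imputed and classed as unknown". On relatedness: "Related events are defined as events that are ticked as suspected by investigator in eCRF". When a patient has several records of the same event, the highest grade is kept in the order "Grade 5 > Grade 4 > Grade 3 > Grade 2 > Grade 1 > missing > not applicable", and for causality "the most serious causality (related > not related) will be chosen". The causality order has two levels and no place for a missing value.

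SAP 5.12 (Missing Values – Missing Visits) is the general rule behind this. It treats missing data as missing at random and adds: "There is no intention to implement any procedure for replacing missing data". It does not mention AEs.

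Other missing fields are handled differently. SAP 5.8.1 says: "AEs that have missing onset dates will be considered to be treatment-emergent", unless the stop date shows that the event ended before first dose. A partial onset date is taken as the latest possible date when deciding treatment emergence. SAP 5.5 takes a medication with an unclear start date to be concomitant.

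Protocol 14.2.2 promises AE summaries by grade and by relationship but gives no rule for a missing value of either.

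**The concern.** Safety and tolerability is the primary objective of the Run-in Cohort, Arm B and Arm C (SAP 2.1.1, 2.3.1, 2.4.1), and SAP 5.8 plans no formal safety analysis, so the descriptive counts are the result. A blank causality field cannot satisfy the definition of related, and a blank grade cannot reach Grade 3. Each blank can therefore only lower the tables that use that field, which is the direction favourable to the drug. For a missing onset date the SAP takes the cautious side. Its list of tables includes no count of unknowns and no sensitivity table that would show a reader how much could be hidden. In the combination arms each AE has two causality fields, because Protocol 13.3.2 requires causality to be judged separately for each treatment. The arms are small enough for one patient to be visible in a percentage.

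**Working it through.** The documents state no figure that depends on this rule, so there is none to reproduce. The check traces the rules to the tables and then sizes one affected patient.

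**Step 1: which tables lose the event.** Inputs: the definitions in SAP 5.8.1, the table list in SAP 6.1.3.1 and the listings in SAP 6.2.

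| Missing field | Left out of | Kept in |
|---|---|---|
| Causality to BGB324 | 14.3.1.2.3, 14.3.1.3.3, 14.3.1.5.2 | Overall AE tables; SAE tables if serious; 14.3.1.5.1 if Grade 3 or higher; AE listing |
| Causality to erlotinib | 14.3.1.2.4, 14.3.1.3.4, 14.3.1.5.3 | As above |
| Grade | 14.3.1.5.1, 14.3.1.5.2, 14.3.1.5.3 | Overall AE tables; SAE tables if serious; 14.3.1.2.3 and 14.3.1.2.4 if ticked as suspected; AE listing |

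**Step 2: direction.** Leaving an event out can lower the count of patients in a table or leave it unchanged. It leaves the count unchanged when the patient has another qualifying event. For repeats of the same event, the rule of highest grade and strongest causality also keeps the patient in.

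**Step 3: size of one patient.** The planned arm sizes come from SAP 4.1: Run-in 6, Arm A 18, Arm B up to 25, Arm C up to 14. For one affected patient with no other qualifying event, the step is 100/N:
- Run-in: 100/6 = 16.7 points
- Arm A: 100/18 = 5.6 points
- Arm B: 100/25 = 4.0 points
- Arm C: 100/14 = 7.1 points

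If 0 to 3 such patients occur in Arm B (an assumption), the range is 0 to 3 × 4.0 = 12 points.

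**Step 4: expected shortfall under an assumed missing rate.** Neither the missing rate m nor the true rate is in the documents. Assume Arm B with N = 25, a true patient rate of 40% (10/25) and one qualifying event per patient. The expected tabulated rate is 40% × (1 − m):
- m = 0: 40.0%
- m = 1%: 39.6%, a shortfall of 0.4 points
- m = 5%: 38.0%, a shortfall of 2.0 points
- m = 10%: 36.0%, a shortfall of 4.0 points

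The related Grade 3 or higher tables need both fields. If each is missing independently with probability m, the share of qualifying events lost is 1 − (1 − m)²: 2.0% at m = 1%, 9.8% at m = 5% and 19.0% at m = 10%.

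**The case against.** The strongest reply is that the protocol already guards against these blanks. Protocol 13.1.2 requires an assessment of seriousness, severity and causality for every recorded AE. Protocol 13.3.2 asks for an entry of either suspected or not related for each drug. Protocol 16.3 provides for source verification, and Protocol 14 places database lock after all data are reconciled. This stands, and it is why the effect may be zero. But the SAP foresees missing severity and causality by writing a rule for them, and a duty to collect a value does not settle how to count when it is absent.

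A second reply is that the related and Grade 3 or higher tables are listed as subsets (SAP 5.8.1.1), that the safety endpoint is treatment-emergent AEs regardless of causality, and that no decision threshold depends on these rates. This is correct and limits the consequence.

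A third reply is that the onset-date rule decides whether an event enters the tables at all, whereas grade and causality only classify events already counted. That is fair: the rules for different fields differ in direction but do not contradict each other.

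A fourth reply concerns the remedy. Coding every ungraded AE as Grade 3 in the main tables would bias them upward, and in Arm A Cycle 1 it could produce apparent dose-limiting toxicities (DLTs) with no matching DLT record. This also stands, and the fix below avoids it. Counting missing causality as related may credit some erlotinib events to BGB324, which is why the number so assigned must be shown.

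**Conclusion.** The point holds as a gap in the counting rules of SAP 5.8.1. If causality or grade is still missing at lock, the related and Grade 3 or higher AE tables may understate toxicity, and the rule cannot push them the other way. The size is 4.0 points in Arm B and 7.1 points in Arm C for each affected patient with no other qualifying event, assuming full planned enrolment. The number of such patients is unknown and may be zero.

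A reader might infer more than the documents support:
- *That these events disappear from every related and every Grade 3 or higher table, or from the safety report.* Each blank removes an event only from tables that use that field. The laboratory and QTcF grade tables (SAP 6.1.3.2 and 6.1.3.4) summarise laboratory and ECG results rather than AE forms.
- *That missing causality is treated as not related.* The SAP makes it a separate unknown class, though that class does not feed the related tables.
- *That toxicity is in fact understated.* This needs blanks to occur and some of them to be truly related or Grade 3 or higher; the documents give no evidence of either.
- *That SAP 5.12 is itself the fault.* It is a general sentence; the rule that matters is in 5.8.1.

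This is a cheap improvement to a stated rule and does not invalidate the safety analysis.

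**What to change.** In SAP 5.8.1:
- Query blank causality and grade before database lock.
- In the related-AE tables (including related SAEs and related Grade 3 or higher), count an AE with causality still missing as related to each study drug the patient had received. Footnote the number of events assigned this way.
- In the Grade 3 or higher tables, keep the observed grades as the main result, show an unknown-grade row, and add a worst-case sensitivity count that treats a missing grade as Grade 3.
- Leave DLT determination and the listings unchanged, with the values shown as missing.

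In SAP 5.12, add an exception for what 5.5 and 5.8.1 state. The existing rules there for unclear medication dates and missing AE onset dates already sit awkwardly with its blanket sentence.

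The cost is a few sentences in the SAP, a derived variable, footnotes and one sensitivity count. If nothing is missing, no result changes. The downside is that reported related-AE rates may be slightly less favourable and may include some events that are truly unrelated.

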5.13 Deviations from SAP

Any deviations from the original statistical plan will be described and justified in the final clinical study report, whether written post interim or final analysis.

5.14 Changes in Conduct or Planned Analyses from the Protocol

There have been no other changes in analyses from those defined in the protocol.

5.15 Algorithms/SAS Codes

- **Tables that need descriptive statistics – continuous variables:**

```
PROC UNIVARIATE DATA=dset NOPRINT;  
  VAR var1 var2 var3 ...varn;  
  BY byvar; (optional)  
  OUTPUT OUT=outname  
  N=n MEAN=mean MIN=min MAX=max MEDIAN=median STD=std *Q1=q1 Q3=q3;  
  RUN;
```

- **Tables that need frequency counts:**

```
PROC FREQ DATA=dset NOPRINT;  
  BY byvar; (optional)  
  TABLES var1 *var2;  
  OUTPUT OUT=outname;  
  RUN;
```

- **Tables that need life table with estimates of survival, with CIs:**

```
PROC LIFETEST DATA=dset OUTSURV=LIFE METHOD=KM;  
  BY treatment;  
  TIME duration*censor (0 or 1);  
  RUN;
```

- **Tables that need 95% CIs within group for binomial proportions:**

```
PROC FREQ DATA=dset;  
  BY byvar; (optional)  
  TABLES var1/binomial (p=.05) alpha=0.05;  
  EXACT BINOMIAL;  
  RUN;
```

```
PROC FREQ data=dset order=freq;  
  TABLES var / binomial(ac wilson exact) alpha=.05;  
  WEIGHT Count;  
  run;
```

6 Tables and Listings

6.1 Table Format

All output will be produced using SAS version 9.2 or a later version.

In the top left portion of each table/listing, a *table/listing number* followed by the *title* of the table/listing will be presented. After the title line, optional *sub-title* or *population* information can be presented. Horizontal lines will appear before and after the column heading of the table/listing. *Footnotes* will be put under the main body of text at the bottom of the page.

The *sponsor name*, *protocol number*, programmers User ID, status of the table/listing (i.e. draft or final) and *SAS program name* will appear bottom left in a string and the *page number* will appear on the bottom right corner of each table/listing. The *date and time of creation* of table/listing will appear bottom left under the sponsor name. The source listing number will appear bottom left.

A *landscape layout* is proposed for both table and listing presentations.

The *left and right margins* of all tables and listings will be a minimum of 2.1 cm from the left and 1.9cm from the right. The *top and bottom margins* will be a minimum 2.92cm. *Header and footer* will be both 1.27 cm.

There is no special requirement of *font type* and *size*, but an *8-point* font size for tables and *7-point* for listings is proposed using *Courier New* font. A maximum SAS line size=141 and page size=44 for *8-point* font size, and line size=161 and page size=50 for *7-point* will be used so as to fit on both UK and US paper sizes.

In a listing, in the case that a subject's record has been continued to the next page, an appropriate identification (e.g., the subject ID number) must be presented at the beginning of that page.

6.2 Conventions

Unless otherwise specified, in summary tables of continuous variables, the minimum and maximum values will be displayed to the same number of decimal places as the raw data, the mean and median will be presented to one extra decimal place compared to the raw data, and the standard deviation will be displayed to two extra decimal places compared to the raw data. Wherever possible data will be decimal aligned.

Unless otherwise specified frequency tabulations will be presented by number and percentage, where the percentage is presented in parenthesis to 1 decimal place.

P-values, if applicable, will be presented to 3 decimal places. If a p-value is less than 0.05 but is greater than or equal to 0.01, then an asterisk (*) will be added next to this value. If a p-value is less than 0.01 but is greater than or equal to 0.001, then two asterisks (**) will be added next to this value. Finally, if the p-value is less than 0.001 then three asterisks (***) will be added next to this value and it will be presented as <0.001. If the rounded result is a value of 1.000, it will be displayed as >0.999. Any date information in the listing will use the *date9.* format, for example, 07MAY2002. In the listing, a unit associated with a variable will be presented only once within parentheses either below or next to that variable in the heading portion. If a parameter has multiple units, each unit will be displayed only once, as applicable.

All tables will have their source listing referenced in a footnote. Listings should be sorted by treatment group, subject and visit and have the source data received by data management referenced in a footnote. All tables and listings will be converted into Microsoft Word documents and collated into two complete documents.

6.1 Tables

6.1.1 Section 14.1: Demographic and baseline

Table 14.1.1.1	Subject Disposition (Enrolled Population)
Table 14.1.1.2	Important Protocol Violations (Enrolled Population)
Table 14.1.2	Demographics (Safety Population)
Table 14.1.3	Cancer History (Safety Population)
Table 14.1.4	Medical History (Safety Population)
Table 14.1.5	Prior Cancer Therapies (Safety Population)
Table 14.1.6.1	Prior Medications (excluding anti-cancer therapies)
Table 14.1.6.2	Concomitant Medications (Safety Population)
Table 14.1.7.1	Summary of Exposure to BGB324 (Safety Population)
Table 14.1.7.2	Summary of Exposure to Erlotinib (Safety Population)
Table 14.1.7.3	Summary of Exposure : Number of participants by cycle (Safety Population)
Table 14.1.7.4	Summary of dose modification during the study (Safety Population)
Table 14.1.7.5	Summary of Erlotinib dose modification during the study (Safety Population)
Table 14.1.8	Compliance (Safety Population)

6.1.2 Section 14.2: Primary and secondary

Table 14.2.1	Assessment of anti-tumour activity – Best Overall Response (Confirmation not Required) (Efficacy Population)
Table 14.2.2	Assessment of anti-tumour activity – Sum of Target Lesions Measurement (Efficacy Population)
Table 14.2.3	Time to progression (TTP) – Kaplan-Meier Analysis (Efficacy Population)

6.1.3 Section 14.3: Safety

6.1.3.1 Adverse events

Table 14.3.1.1	Summary of Adverse Events (Safety Population)
Table 14.3.1.2.1	Adverse Events by System Organ Class and Preferred Term (Safety Population)
Table 14.3.1.2.2	Adverse Events by System Organ Class, Preferred Term, and CTCAE Grade (Safety Population)
Table 14.3.1.2.3	Adverse Events Related to BGB324 by System Organ Class and Preferred Term (Safety Population)
Table 14.3.1.2.4	Adverse Events Related to Erlotinib by System Organ Class and Preferred Term (Safety Population)
Table 14.3.1.2.5	Adverse Events by System Organ Class, Preferred Term and Severity of CTCAE Grade (Safety Population)
Table 14.3.1.3.1	Serious Adverse Events by System Organ Class and Preferred Term (Safety Population)
Table 14.3.1.3.2	Serious Adverse Events by System Organ Class, Preferred Term, and Severity of CTCAE Grade (Safety Population)
Table 14.3.1.3.3	Serious Adverse Events Related to BGB324 by System Organ Class and Preferred Term (Safety Population)
Table 14.3.1.3.4	Serious Adverse Events Related to Erlotinib by System Organ Class and Preferred Term (Safety Population)
Table 14.3.1.4.1	Adverse Events Leading to Discontinuation by System Organ Class and Preferred Term (Safety Population)

Table 14.3.1.5.1	Adverse Events with CTCAE Grade ≥ 3 by System Organ Class and Preferred Term (Safety Population)
Table 14.3.1.5.2	Adverse Events \geq Grade 3 Related to BGB324 by System Organ Class and Preferred Term (Safety Population)
Table 14.3.1.5.3	Adverse Events \geq Grade 3 Related to Erlotinib by System Organ Class and Preferred Term (Safety Population)
Table 14.3.1.6.1	Adverse Events Occurring $\geq 10\%$ by System Organ Class and Preferred Term (Safety Population)
Table 14.3.1.7.1	Adverse Events leading to death by System Organ Class and Preferred Term (Safety Population)
Table 14.3.1.8.1.1	Summary of DLTs occurring during the study (Safety Population)

6.1.3.2 Laboratory results

Table 14.3.5.1.1	Laboratory Results – Hematology - Summary and Change from Baseline (Safety Population)
Table 14.3.5.2.1	Laboratory Results – Coagulation - Summary and Change from Baseline (Safety Population)
Table 14.3.5.3.1	Laboratory Results –Chemistry - Summary and Change from Baseline (Safety Population)
Table 14.3.5.4.1	Laboratory Results for subjects with CTCAE \geq Grade 3 (Safety Population)
Table 14.3.5.4.2	Laboratory Results CTCAE Grade ≥ 3 (Safety Population)

6.1.3.3 Vital signs

Table 14.3.6.1.1	Vital Signs - Summary and Change from Baseline (Safety Population)
------------------	--

6.1.3.4 ECG

Table 14.3.6.2.1	ECG Results - Summary and Change from Baseline (Safety Population)
Table 14.3.6.2.2	ECG Results - Overall Interpretation (Safety Population)
Table 14.3.6.2.3	QTcF (ms) by CTCAE Grade and Dose (Safety Population)
Table 14.3.6.2.4	Maximum QTcF Increase from Baseline (Safety Population)

6.1.3.5 ECOG Performance Status

Table 14.3.6.3.1	Eastern Cooperative Oncology Group (ECOG) Performance Status (Safety Population)
------------------	--

6.2 Listings

- Listing 16.1.7.1 Dose Escalation Cohort Assignment (Safety Population)
- Listing 16.1.7.2 Drug Accountability (Safety Population)
- Listing 16.2.1.1 Subject Disposition (Enrolled Population)
- Listing 16.2.1.2 Inclusion/Exclusion Descriptions (Enrolled Population)
- Listing 16.2.1.3 Inclusion/Exclusion Criteria Not Met (Enrolled Population)
- Listing 16.2.2.1 Important Protocol Deviations (Enrolled Population)
- Listing 16.2.3 Subjects Excluded from the Analysis Sets (Enrolled Population)
- Listing 16.2.4.1 Demographics (Safety Population)
- Listing 16.2.4.2 Cancer History (Safety Population)
- Listing 16.2.4.3 Medical History (Safety Population)
- Listing 16.2.4.4 Mutation Status (Safety Population)
- Listing 16.2.4.5.1 Prior Cancer Therapy (Safety Population)
- Listing 16.2.4.5.2 Prior Erlotinib Administration at Screening (Safety Population)
- Listing 16.2.4.6 Prior Cancer-related Surgery (Safety Population)
- Listing 16.2.4.7 Prior and Concomitant Medications (Safety Population)
- Listing 16.2.4.8.1 Physical Examination - Complete (Safety Population)
- Listing 16.2.4.8.2 Physical Examination – Symptom Directed (Safety Population)
- Listing 16.2.4.9 ECOG Performance Status (Safety Population)
- Listing 16.2.5.1 BGB324 Exposure (Safety Population)
- Listing 16.2.5.2 Erlotinib Exposure (Safety Population)
- Listing 16.2.5.3 BGB324 Administration (In-Clinic) (Safety Population)
- Listing 16.2.5.4 BGB324 Administration (By Cycle) (Safety Population)
- Listing 16.2.5.5 Erlotinib Administration (Safety Population)
- Listing 16.2.6.1 Tumour Assessment – Target Lesions (Safety Population)
- Listing 16.2.6.2 Tumour Assessment – Non-Target Lesions (Safety Population)
- Listing 16.2.6.3 Tumour Assessment – New Lesions (Safety Population)
- Listing 16.2.6.4 Assessment of anti-tumour activity (Safety Population)
- Listing 16.2.6.5 Time to progression details
- Listing 16.2.7.1 Adverse Events (Safety Population)
- Listing 16.2.7.2 Serious Adverse Events (Safety Population)
- Listing 16.2.7.3 Adverse Events Related to BGB325 (Safety Population)
- Listing 16.2.7.4 Adverse Events Related to Erlotinib (Safety Population)
- Listing 16.2.7.5 Adverse Events Leading to Discontinuation (Safety Population)
- Listing 16.2.7.6 Adverse Events – Dose Limiting Toxicities (Safety Population)
- Listing 16.2.7.7 Adverse Events \geq Grade 3 (Safety Population)
- Listing 16.2.7.8 List of DLTs (Safety Population)
- Listing 16.2.8.1.1 Laboratory Results: Hematology (Safety Population)
- Listing 16.2.8.1.2 Laboratory Results: Coagulation (Safety Population)
- Listing 16.2.8.1.3 Laboratory Results: Chemistry (Safety Population)
- Listing 16.2.8.1.4 Laboratory Results: Urinalysis (Safety Population)
- Listing 16.2.8.1.5 Laboratory Results: Urine/Serum Pregnancy Test
- Listing 16.2.8.1.6 Clinically Significant Laboratory Results (Safety Population)
- Listing 16.2.8.1.7 Laboratory Results for patients with CTCAE Grade \geq 3 (Safety population)

Listing 16.2.8.2.1

Vital Signs (Safety Population)

Listing 16.2.8.3.1

ECG Results (Safety Population)

Maximum increase in QTcF, by CTCAE Grade and Treatment (safety population)

Listing 16.2.8.4.1

Echocardiogram/Muga Scan (Safety Population)

Listing 16.2.8.5.1

